University of Kansas Medical Center
RESEARCH PROTOCOL INVOLVING HUMAN SUBJECTS
TEMPLATE WITH GUIDANCE

Version date: April 25, 2019

Principal Investigator: [name], MS

Study Title: An open label trial of cryoneurolysis for improvements in pain, activities of daily living and quality of life in patients with ankle osteoarthritis.

I. Purpose, Background and Rationale

A. Aim and Hypotheses

This will be an open-label trial to describe the effects of cryoneurolysis with iovera on symptom relief in patients with painful Kellgren-Lawrence (KL) grade 2–4 ankle osteoarthritis (OA). The Foot and Ankle Outcome Score (FAOS) subscales will be used to assess outcomes at 6, 12 and 24 weeks after treatment.

The aim of this study is to assess clinically significant long-term symptomatic relief with cryoneurolysis in people with unilateral ankle osteoarthritis (OA).

Depending on the location of pain, we will treat either 1) the Superficial Fibular Nerve (SFN), Sural Nerve (SN) and Saphenous Nerve or 2) the deep fibular nerve with cryoneurolysis using the iovera device. The primary study endpoint, clinically significant improvement in pain 12 weeks after each treatment, will be assessed using the FAOS-Pain subscale.

The secondary outcomes will be improvement in quality of life (FAOS-QoL), activities of daily living (FAOS-ADL) and Numerical Rating Scale (NRS) for pain.

The tertiary outcome will be improvement in physical performance measures (40m fast-paced walking test, Standing Balance Test).

We hypothesize that people with painful ankle OA will experience significant improvement in pain, activities of daily living, quality of life and physical performance for at least 12 weeks following treatment. Based on research done using iovera in patients with knee osteoarthritis, we anticipate that it will have a greater magnitude and duration of analgesic effect along with significantly fewer adverse events compared with the rates reported for standard of care therapy (i.e. corticosteroid injection).^{1,2}

Specific Aim 1: To determine the extent of pain relief after cryoneurolysis of nerves innervating the ankle joint in patients with ankle osteoarthritis.

Primary Hypothesis 1: Cryoneurolysis of nerves innervating the ankle joint in patients with ankle OA results in reduction in ankle pain (FAOS-Pain) detectable at the following post-treatment time points:

- a) 6 weeks
- b) 12 weeks (primary outcome)
- c) 24 weeks

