Specific Aim 2: To determine the extent of improvement in activities of daily living (ADL) and quality of life (QOL) after cryoneurolysis of nerves innervating the ankle joint in patients with ankle osteoarthritis.

Hypothesis 2a: Cryoneurolysis of nerves innervating the ankle joint in patients with ankle OA results in improved ADL (FAOS-ADL) detectable at the following post-treatment time points:

- a) 6 weeks
- b) 12 weeks
- c) 24-weeks

Hypothesis 2b: Cryoneurolysis of nerves innervating the ankle joint in patients with ankle OA results in improved QOL (FAOS-QOL) detectable at the following post-treatment time points:

- a) 6 weeks
- b) 12 weeks
- c) 24-weeks

Specific Aim 3: To determine the extent of improvement in physical performance measures (40m fast-paced walking test and Standing Balance Test) after cryoneurolysis of nerves innervating the ankle joint in patients with ankle osteoarthritis.

Hypothesis 3a: Each cryoneurolysis treatment results in improved physical performance detectable at the following post-treatment time points:

- a) 6 weeks
- b) 12 weeks
- c) 24-weeks

B. Background and Significance

Approximately 15% of the world's adult population is affected by joint pain and disability resulting from osteoarthritis (OA), and approximately 1% have OA of the ankle. There has been substantial clinical and basic science research related to hip and knee OA. However, research related to ankle OA is sparse.³ Although the hip and knee joints are most commonly affected by primary OA, at the ankle, OA is most commonly post-traumatic. Traumatic ankle injuries that may result in OA include fractures of the malleoli, tibial plafond, talus, isolated osteochondral damage of the talar dome, and ankle ligament injuries.

OA of the ankle (tibiotalar) joint progresses from early damage to diffuse and severe degeneration and deformity of the joint. The leading causes include trauma, ischemia, abnormal ossification, and genetic predisposition. Although trauma is probably the most common cause of injury and degeneration of the ankle (70% of reported cases), repetitive microtrauma could also be a contributing factor. Despite the high prevalence of ankle trauma and related chondral lesions, the rate of symptomatic and disabling OA is lower than that of the hip and knee, due to the different biologic and biomechanical characteristic of the cartilage and subchondral bone at the ankle⁴.

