FAOS (Pain, ADL, QoL), NRS for pain and physical performance tests (40 m fast paced walking test and, Standing Balance Test) will be assessed at baseline and 6, 12, and 24 weeks post-treatment. Phone calls at 3, 9 and 18 weeks post-treatment will monitor subjects using the NRS pain scale.⁷ Electronic data capture will be used for this study. Adverse events will be monitored at each telephone call and follow-up visit. There will be a grace period of 21 days between the screening and treatment visit. There is a +/- 3-day window for follow-up visits. During the time period of March to May, 2020(depending on duration of suspension of non-essential research), we are modifying the protocol to conduct virtual study visits to address the COVID-19 pandemic. The following data points will be or will not be collected during this time as per the individual circumstance: 40mFPWT or Standing Balance test at 6 week, 12 week, and 24 week. In order to ensure subject safety and welfare we will conduct the 6 week, 12 week and 24 week f/u visit remotely for each treatment arm as per KU essential research guidelines. We will also offer participants masks, gloves, and complete the f/u visit at the

earliest to limit any potential exposure to people in the hospital. In order to address data integrity issues, we will try to conduct the 12 week f/u visits in person.

[figure not shown]

Figure 2 – Protocol flowchart depicting criteria for responders and non-responders at each follow up time point.

C. Sample size and power calculation

In this open-label study, participants will undergo cryoneurolysis using iovera. FAOS (Pain, ADL, QoL), NRS for pain and physical performance tests (40m fast-paced walking test and Standing Balance Test) data will be collected at baseline and 6, 12 and 24 weeks post-treatment. A 24-week follow-up duration was selected to detect meaningful differences from standard of care and long-term effects. A control group will not be included in this initial pilot study. Differences between each of the three follow-up time points and baseline will be assessed using one-sample t-tests or repeated measures analyses, as appropriate, controlling for study-wide alpha level to account for multiple comparisons as well as 6-week and 24-week analyses.

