A FAOS validation study, completed by S.B.Mani et al., confirmed that some FAOS sub-scales (i.e. pain, activities of daily living and quality of life) are valid for independent use. According to the study, the effect size for FAOS pain and quality of life is 1.06, whereas for activities of daily living there is an effect size of 0.65. At an effect size of 0.65 and a single-sized alpha of 0.025, a sample size of 32 would provide a power of 90%. While 80% power is customary, it would be desirable to plan for 90% to reduce the probability of missing an effect if one is present and to provide sufficient power for comparisons at 2-time points. Assuming up to 20% dropout, we plan to recruit 40 participants. This should be more than sufficient, considering that the effect size for the other 2 outcomes has been reported to be 1.06.⁹

D. Subject Criteria (See Vulnerable Populations appendix, if applicable):

Enrollment will be comprised of 40 subjects, age 18 and over with symptomatic ankle OA. There will be no exclusions based on sex or ethnic group. Potential subjects will be identified through hospital records, referrals from physicians in the surrounding community, and mass mailings, or advertisements posted in area clinics and businesses.

1. Inclusion criteria

- Participation in an institutional review board-approved informed consent process, culminating in providing written consent.
- Willingness and ability to comply with the study procedures, visit schedules and ability to follow verbal and written instructions.
- Male or female over 18 years of age.
- Currently Kellgren-Lawrence (KL) Grade 2, 3 or 4 in the ankle based on an X-ray. (weight-bearing mortise views with 20° internal rotation)¹⁰
- Limited by unilateral ankle pain, rated on a Numerical Rating Scale for pain severity as ≥5 on most days over the last month.
- Foot and ankle outcome score (FAOS) of < 75 in at least 1 category.
- Body mass index (BMI) ≤ 50 kg/m²
- Ambulatory.
- Willingness to abstain from the use of protocol-restricted medications during the study and also willing to abstain from using analgesics other than acetaminophen 1 week prior to the beginning of the study.
- Has undergone at least one prior conservative osteoarthritis treatment (e.g. physical therapy, analgesics).

2. Exclusion criteria:

- Baseline knee, hip, spine or other limitations that affect the walking ability to a greater extent than their ankle.

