All participants will be assigned to undergo cryoneurolysis using iovera. FAOS (Pain, ADL, QoL), NRS for pain and physical performance test (40 m fast paced walking test, standing balance test) data will be collected at baseline, 6 weeks, 12 weeks and 24 weeks. A 24-week follow-up duration was selected to detect meaningful differences from standard of care and long-term effects, while minimizing the variability that may occur further out from baseline. Differences between each of the three follow-up time points for each of the interventions (superficial and deep) and baseline will be assessed using one-sample t-tests or repeated measures analyses, as appropriate. This will control for study-wide alpha level to account for multiple comparisons as well as 6-week and 24-week analyses. A soft-lock of the database will occur after the 6- and 12-week time-points.

- B. Outcome:** We expect statistically significant and clinically meaningful improvement in pain, activities of daily living, quality of life and physical performance with iovera[®] in people with ankle OA at 12 weeks post-treatment.
- C. Study results to participants:** The study will be registered on www.clinicaltrials.gov and results posted upon completion of the study.
- D. Publication Plan:** Results will be submitted for presentation at an appropriate conference and for publication in an appropriate journal for the topic of study.

VI. Bibliography / References / Literature Cited

5. Trescot AM. Cryoanalgesia in interventional pain management. *Pain Physician* 2003;6:345-60.

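### The 90% power in II.C is for one test on 32 participants with no nerve group named; it does not carry over to the separate superficial and deep FAOS-ADL tests in V.A

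*Combined protocol and SAP*

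**What the plan says.** Section II.C takes standardised effects from a cited FAOS validation study (1.06 for pain and quality of life, 0.65 for activities of daily living) and sizes on the smallest: "At an effect size of 0.65 and a single-sized alpha of 0.025, a sample size of 32 would provide a power of 90" per cent. It adds that 90% rather than 80% is wanted partly to cover comparisons at two time points. Then: "Assuming up to 20% dropout, we plan to recruit 40 participants". Both 32 and 40 are whole-trial numbers.

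The analysis sentence in II.C names no nerve group: "Differences between each of the three follow-up time points and baseline will be assessed using one-sample t-tests or repeated measures analyses". Primary Hypothesis 1 and Hypothesis 2a in I.A, and the primary endpoint sentence in II.E, name none either.

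V.A repeats that analysis sentence with an insertion: "Differences between each of the three follow-up time points for each of the interventions (superficial and deep) and baseline will be assessed". This is not a stray phrase. I.A places the primary endpoint 12 weeks after each treatment, Hypothesis 3a concerns each cryoneurolysis treatment, and the objective in II.A refers to each superficial and deep treatment.

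The first treatment goes to one nerve group, chosen by pain location (I.A). Non-responders are to have the other group treated (II.B), and the second course has its own FAOS schedule (second table in II.E). No expected split, number of second courses or per-intervention power is given.

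**The concern.** The two analysis sentences describe different tests, and only one matches the power statement. If V.A governs, each test rests on part of the 32 unless many participants contribute to both interventions, and the plan does not say what power those tests have.

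The stake is interpretation. II.C aims at 90% so that a real effect is unlikely to be missed, and V.B expects statistically significant improvement in activities of daily living. A null FAOS-ADL result for one nerve group could be read as evidence against benefit, on the strength of a 90% that belongs to another test.

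**Working it through.** **Inputs.** From II.C: d = 0.65 (FAOS-ADL), d = 1.06 (FAOS-Pain, FAOS-QoL), alpha 0.025, 32 evaluable, 40 recruited. The wording on sidedness is garbled, so both readings are shown. The split between nerve groups is not in the documents; any split below is an assumption.

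**Formula.** One-sample t-test on change from baseline, exact noncentral t: power = 1 − F(t_crit; df = n − 1, noncentrality d√n). The tail area for t_crit is 0.025 (one-sided) or 0.0125 (two-sided).

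**Step 1: reproduce the plan's figures.** For d = 0.65 and n = 32, noncentrality = 0.65 × √32 = 3.68.
- One-sided 0.025: t_crit = 2.040, power 94.5%; 90% would need n = 27.
- Two-sided 0.025: t_crit = 2.356, power 90.0%; 90% needs exactly n = 32.
- Dropout: 32 / (1 − 0.20) = 40.

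The stated 90% is exact on the two-sided reading and conservative on the one-sided reading.

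**Step 2: V.A's tests, first treatments only.** Each participant is in one group, so the smaller group has at most 32/2 = 16, or 40/2 = 20 with no dropout. Power, one-sided / two-sided 0.025:

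| n in group | FAOS-ADL, d = 0.65 | FAOS-Pain, d = 1.06 |
|---|---|---|
| 20 (even split of 40) | 79% / 68% | 99% / 98% |
| 16 (even split of 32) | 68% / 56% | 98% / 95% |
| 12 (assumed) | 54% / 40% | 92% / 84% |
| 8 (assumed) | 36% / 24% | 73% / 59% |

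At 16 per group the chance of missing a true FAOS-ADL effect of 0.65 is 1 − 0.68 = 32% or 1 − 0.56 = 44%, against the intended 10%. A variance estimate shared across groups raises FAOS-ADL power only to 71% / 60% (n = 16) or 81% / 72% (n = 20).

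For FAOS-Pain, 90% needs 12 (one-sided) or 14 (two-sided) per group.

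**Step 3: second courses counted.** For FAOS-ADL, 90% needs 27 (one-sided) or 32 (two-sided) per intervention. With 32 evaluable, the number contributing to both must be at least 2 × 27 − 32 = 22 (69%), or 2 × 32 − 32 = 32 (all). This holds whatever the first-treatment split, and it assumes the same effect in second courses.

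**Step 4: alpha.** The plan promises "controlling for study-wide alpha level to account for multiple comparisons as well as 6-week and 24-week analyses" but names no method. As an illustration only, halving 0.025 to 0.0125 for two interventions gives, at n = 16, 56% / 43% for FAOS-ADL and 95% / 90% for FAOS-Pain; at n = 12, FAOS-Pain has 84% / 74%.

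**The case against.** **Second courses may well count.** The references to each treatment and the full second-course FAOS schedule point that way, and the flowchart (Figure 2) is not visible in the text available. II.B checks response out to 24 weeks while I.B expects about 90 days of relief, so second courses could be numerous. This stands: the first-treatments-only figures are one reading, not the established one. It does not restore the 90%, since the plan does not assume the 22 or 32 double contributors required, nor an unchanged effect in people whose first treatment failed or wore off.

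**The alpha may already be adjusted.** II.C mentions two time points, and the 90% reproduces at two-sided 0.025, which could be 0.05 halved. This also stands: 0.025 cannot be called unadjusted, and a further reduction might partly double-count.

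**The consequence is limited.** II.C does not claim 90% for nerve-specific tests, FAOS-ADL is secondary, and the protocol says "A control group will not be included in this initial pilot study". All true, and this is why the remedy is text only.

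**The test may be a repeated-measures model.** Both sections allow it. Its power cannot be computed from the documents, so the figures apply to the one-sample t-test.

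**Conclusion.** The point holds as an inconsistency between II.C and V.A. The 90% describes one test on 32 participants and is not delivered by separate superficial and deep FAOS-ADL tests. On first treatments only, with one-sample t-tests at alpha 0.025, the smaller group has at most 68% / 56% (one-sided / two-sided) with 32 evaluable and 79% / 68% with 40. With second courses, both tests reach 90% only if at least 22 of 32 (one-sided) or all 32 (two-sided) contribute to both with an unchanged effect.

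Three stronger readings are not supported:
- A reader might infer that the 90% was miscalculated. It reproduces; the issue is which test it covers.
- A reader might infer that the trial is underpowered for its primary outcome. FAOS-Pain has 98% / 95% at 16 per group. It falls below 90% only if a group has fewer than 12 (one-sided) or 14 (two-sided), or if further alpha adjustment is severe enough for the group size.
- A reader might infer that the pooled test is the right one and the nerve-specific tests should be demoted. The hypotheses for pain and activities of daily living name no nerve group, but I.A, Hypothesis 3a, II.A and V.A speak of each treatment or intervention. That choice belongs to the sponsor.

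**What to change.** Reconcile II.C with V.A by stating which analysis the 90% covers.
- **If pooled over nerve groups:** limit the 90% to that test and report superficial and deep results as estimates with 95% confidence intervals.
- **If per intervention:** replace the 90% for FAOS-ADL with the per-group power and its assumptions, for example 68% one-sided or 56% two-sided for an even split of 32 on first treatments, and lower in a smaller group.

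In either case, say whether 0.025 is one- or two-sided and whether it is already adjusted for the two time points. State before data are seen whether second courses enter the week-12 analysis.

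The cost is a few sentences in II.C and V.A and one prespecified decision, with no increase in enrolment. The downside is a less favourable stated power for nerve-specific FAOS-ADL.

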The cryoneurolysis mechanism of action is well-understood and established in prior studies.⁵ Results of a recent study demonstrate that cryoneurolysis can alleviate the pain and symptoms of knee OA for up to 90 days¹. Pharmacologic and surgical options for ankle OA are limited. Using cryoneurolysis in patients with ankle OA could potentially provide immediate symptomatic relief with a greater duration of analgesia and a lower rate of side effects. These potential benefits could reduce the need for both clinic and injection visits when compared to other available treatment modalities, thereby reducing patient and provider burden and health care expenditures.

II. Research Plan and Design

A. Study Objectives: The goal of this study is to evaluate the efficacy of cryoneurolysis for improving ankle symptoms and function. Specifically, this study will measure changes in pain, activities of daily living, quality of life and physical performance at 6, 12 and 24 weeks after each superficial and deep treatment.

B. Study Type and Design:

This is a single-site, open-label study of participants with painful ankle OA assigned to undergo cryoneurolysis of either the Superficial Fibular Nerve (SFN), Sural Nerve (SN) and Saphenous Nerve, or the Deep Fibular Nerve (DFN) using ultrasound-guided cryoneurolysis. Subjects will initially undergo diagnostic nerve blocks using 1% lidocaine with epinephrine for either the superficial nerves or the DFN to confirm analgesia prior to the cryoneurolysis procedure.

We will evaluate responder status with NRS at clinic visits 6 weeks, 12 weeks and 24 weeks following treatment as well as NRS via web-form or phone calls (per subject preference) at 3, 9 and 18 weeks. "Non-responders" being defined as anyone reporting less than 20% pain relief with respect to their baseline NRS scores. For subjects who become non-responders, we will treat the other nerve group with iovera at their next clinic visit (e.g. if a subject becomes a non-responder 9 weeks after superficial nerves are treated, then at 12 week follow-up, the participant will be offered treatment of the deep fibular nerve).

Figure 2 depicts the flow of how participants will be treated and potentially offered an alternative treatment if their initial treatment fails to provide durable benefit.

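### The 90% power in II.C is for one group of 32, but V.A tests superficial and deep treatment separately, and the documents disagree on the unit of analysis

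*Combined protocol and SAP*

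**What the plan says.** **Sizing (II.C).** "At an effect size of 0.65 and a single-sized alpha of 0.025, a sample size of 32 would provide a power of 90" percent. The 0.65 is the FAOS-ADL effect size; FAOS-Pain and FAOS-QoL are given 1.06. There is no control group and the tests are one-sample. Dropout of up to 20% raises 32 to 40. The margin over 80% power is justified partly "to provide sufficient power for comparisons at 2-time points". II.C describes the tests without splitting by nerve group.

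**Text that splits by treatment.**
- I.A sets the primary endpoint as "clinically significant improvement in pain 12 weeks after each treatment".
- II.A measures change "at 6, 12 and 24 weeks after each superficial and deep treatment".
- V.A: "Differences between each of the three follow-up time points for each of the interventions (superficial and deep) and baseline will be assessed".

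**Text that does not split.** Hypotheses 1, 2a and 2b (I.A) concern cryoneurolysis of the nerves supplying the ankle, taken together. The primary endpoint sentence in II.E compares FAOS-Pain with baseline at 12 weeks and does not mention nerve group.

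**Allocation and second treatment.** Nerve group follows the location of pain (I.A), so the split is not fixed by design. II.B adds: "For subjects who become non-responders, we will treat the other nerve group with iovera at their next clinic visit".

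**Multiplicity.** II.C promises "controlling for study-wide alpha level to account for multiple comparisons as well as 6-week and 24-week analyses". V.A says of the t-tests or repeated measures analyses: "This will control for study-wide alpha level to account for multiple comparisons as well as 6-week and 24-week analyses". Neither names a procedure.

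**The concern.** A power statement belongs to a particular test in a particular group. II.C gives it for all participants together; V.A carries out the tests within each nerve group, where the numbers must be smaller unless many people receive both treatments. A reader would take 90% as the chance of success for the V.A tests, and for FAOS-ADL it could be far lower. A non-significant ADL result in one nerve group could then be read as lack of effect when the test had little chance of finding one. If the choice between pooled and separate analysis is left until the data are seen, the primary result also depends on that choice.

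Separately, the 90% does not follow from the inputs printed beside it under the most direct reading, so the alpha to be used is unclear.

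**Working it through.** **Inputs.** From II.C: d = 0.65 (ADL), d = 1.06 (Pain), n = 32, alpha 0.025 (the qualifier is read as one-sided), power 90%, dropout 20%. Assumption: d is mean change divided by SD of change; II.C does not define the standardiser.

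**Formula.** One-sample t-test, one-sided alpha a: power = P(T > t(1−a, n−1)), where T is noncentral t with n−1 degrees of freedom and noncentrality d√n.

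**Step 1: the plan's own figure.** d√n = 0.65 × √32 = 3.677.
- One-sided 0.025: critical value 2.040, power **94.5%**. The smallest n for 90% is 27 (n = 26 gives 89.0%).
- One-sided 0.0125 (two-sided 0.025): critical value 2.356, power **90.0%**. The smallest n for 90% is 32 (n = 31 gives 88.9%).
- Dropout: 32 / 0.8 = 40, as stated.

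So 32 and 90% fit one-sided 0.0125. That could be 0.025 divided over two time points, but the documents do not say so. There is another route: if 0.65 is standardised by the baseline SD, with equal SDs at both times, then d for change = 0.65 / √(2(1−r)). At one-sided 0.025 and n = 32, power is 85.3% at r = 0.3, 90.2% at r = 0.4, 94.5% at r = 0.5 and 99.6% at r = 0.7. The documents give no correlation.

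**Step 2: pooled primary.** At d = 1.06 and n = 32, power is 99.99% at 0.025 and 99.98% at 0.0125.

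**Step 3: per intervention.** The documents give no split. The sizes below are assumptions: 16 is an even split of 32, and 10 with 22 is an uneven one. Second treatments are not counted.

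| Evaluable in the intervention | ADL, 0.025 / 0.0125 | Pain, 0.025 / 0.0125 |
|---|---|---|
| 10 | 45.1% / 32.0% | 84.6% / 73.6% |
| 16 | 68.1% / 55.6% | 97.7% / 94.8% |
| 22 | 82.8% / 73.3% | 99.7% / 99.2% |
| Needed for 90% | 27 / 32 | 12 / 14 |

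**Step 4: effect of a multiplicity procedure, as an example.** Three FAOS subscales at three time points, less the primary, leave 3 × 3 − 1 = 8 tests. At the first Holm step the alpha is divided by 8. ADL power at n = 32 pooled is then 76.4% from 0.025, or 67.8% from 0.0125.

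**The case against.** The best defence is that pooling is intended. The hypotheses, the test description in II.C and the endpoint sentence in II.E are all unsplit, and the phrase in I.A about each treatment could mean first and second treatment, since the assessment schedules are laid out as Treatment 1 and Treatment 2. This stands in part: it would be too strong to say that the plan sets every endpoint and test per intervention. But V.A, the analysis section, plainly tests superficial and deep separately, so the conflict remains.

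A reader might infer that the primary endpoint is underpowered unless the nerve groups are pooled. The documents' own effect size does not support that: 16 per intervention gives 97.7% or 94.8% for FAOS-Pain.

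A reader might also infer that enrolment is too low. Ninety percent for ADL in each intervention at one-sided 0.025 would need 2 × 27 = 54 evaluable, and 54 / 0.8 = 67.5, so 68 enrolled. That figure concerns a secondary outcome in what II.C calls an initial pilot, and it assumes that nobody contributes to both interventions, although II.B allows this. It shows what confirmatory ADL tests would cost and is not a shortfall in the primary objective.

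Finally, the 94.5% depends on an undefined standardiser, and read literally the slip is conservative: 32 exceeds the 27 needed. That is right, and it makes the alpha wording the lesser point.

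**Conclusion.** The concern holds as an inconsistency in the unit of analysis. II.C's 90% belongs to a pooled group of 32 and does not carry over to the tests in V.A. At an assumed even split, ADL power is 68.1% at one-sided 0.025 or 55.6% at 0.0125. FAOS-Pain stays above 90% unless one nerve group has fewer than 12 (0.025) or 14 (0.0125) evaluable participants.

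The power arithmetic is a secondary point. With 0.65 as mean change over SD of change and a one-sided test, the printed inputs give 94.5%; the printed result matches one-sided 0.0125. By itself this needs only a wording correction and does not affect the target of 40.

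The per-intervention figures rest on the assumed splits, on the same standardiser, and on no one being counted twice. Second treatments could raise the count per intervention, but they place the same people in both groups, and V.A does not say how those people are handled. The unnamed multiplicity procedure is missing detail; the finding does not depend on it.

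**What to change.** 1. **Reconcile I.A, II.A, II.C, II.E and V.A on the unit of analysis.** Preferred: make FAOS-Pain at week 12 in the pooled group the single primary test, with one value per participant counted from the first treatment, and report superficial and deep results as estimates with 95% confidence intervals. Alternative: if the per-intervention tests stay confirmatory, replace the single 90% with power per intervention at the expected split, keeping enrolment at 40. In either case, state how a week-12 value taken after an earlier second treatment is counted.
2. **In II.C, state one alpha with its matching power**: one-sided 0.025 with 94.5%, or one-sided 0.0125 (two-sided 0.025) with 90%. Say that 0.65 and 1.06 are mean change over SD of change, or, if they are not, give the standardiser and the correlation and recompute. Give FAOS-Pain power separately (over 99.9% pooled at n = 32) and say which two time points are meant.
3. **Any named multiplicity procedure for the secondary tests should start from that same alpha.** The list of tests is the sponsor's choice; Step 4 shows what Holm over eight tests would do to ADL.

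**Cost.** Text changes in II.C and V.A, with matching wording in I.A, II.A and II.E; no change to enrolment or visits. With pooling, the per-intervention results lose confirmatory status. Without it, the stated power becomes less favourable, most visibly for ADL. A formal procedure also lowers power for the secondary tests.
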